10.1.2 Assessment of Adverse Events by the Investigator

10.1.2.1 Severity

The severity of all AEs should be graded according to the Common Terminology Criteria for Adverse Events (CTCAE). Any AEs which are life-threatening or fatal meet the definition of SAEs (Section 10.3). For those AEs not listed in the CTCAE, the following grading system should be used:

- Mild (CTCAE Grade 1): Transient symptoms, awareness of sign/symptom, but easily tolerated and no interference with subject's daily activities.
- Moderate (CTCAE Grade 2): Marked signs/symptoms that interfere with subject's usual activities, but still acceptable.
- Severe (CTCAE Grade 3): Incapacitating signs/symptoms which cause considerable interference with the subject's daily activities, unacceptable.

10.1.2.2 Causality

The relationship of an AE to the administration of the study drug is to be assessed according to the following definitions:

- No (unrelated, not related, no relation) The time course between the administration of study drug and the occurrence or worsening of the AE rules out a causal relationship and another cause (e.g., concomitant drugs, therapies, complications, etc.) is suspected.
- Yes (related) The time course between the administration of study drug and the occurrence or worsening of the AE is consistent with a causal relationship and no other cause (e.g., concomitant drugs, therapies, complications, etc.) can be identified.
 - The definition implies a reasonable possibility of a causal relationship between the event and the study drug. This means that there are facts (evidence) or arguments to suggest a causal relationship.

The following factors should also be considered:

- The temporal sequence from study drug administration-
 - The event should occur after the study drug is given. The length of time from study drug exposure to event should be evaluated in the clinical context of the event.
- Underlying, concomitant, intercurrent diseases-
 - Each report should be evaluated in the context of the natural history and course of the disease being treated and any other disease the subject may have.
- Concomitant drug(s)-
 - The other drugs the subject is taking or the treatment the subject receives should be examined to determine whether any of them might be recognized to cause the event in question.
- Known response pattern for this class of study drug-
 - O Clinical and/or preclinical data may indicate whether a particular response is likely to be a class effect.

- Exposure to physical and/or mental stresses-
 - The exposure to stress might induce adverse changes in the recipient and provide a logical and better explanation for the event.
- The pharmacology and PK of the study drug
 - o The known pharmacologic properties (absorption, distribution, metabolism, and excretion) of the study drug should be considered.

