5 PHARMACOKINETIC AND SAFETY DATA REVIEW

5.1 Ongoing Data Review

All available PK and safety data through Week 10 of the study will be reviewed by the Sponsor and/or the Sponsor's designee (e.g., for unblinded PK data) for the first 10 subjects enrolled into Cohort 1 prior to opening enrollment into the Core Phase for subjects in Cohort 2. Likewise, all available PK and safety data through Week 10 will be reviewed by the Sponsor and/or the Sponsor's designee (e.g., for unblinded PK data) for the first 10 subjects enrolled into Cohort 2, prior to opening enrollment into the Core Phase for Cohort 3. Enrollment will not stop during this data review period.

As the study progresses and data become available, the pediatric PK/PD model will be updated with emerging data in order to confirm the appropriate dose of avatrombopag in each cohort. The PK/PD model will be updated after each age cohort is fully enrolled, but without stopping enrollment for remaining cohorts. The dose of avatrombopag may be modified during the study based on results of the PK and safety data review.

Safety data will be reviewed on an ongoing basis and new enrollment may be paused for any serious unexpected and related AEs that occur (Figure 2).

The exact doses of avatrombopag may be modified during the study based on PK/PD analysis of emerging PK/PD and safety data.

The Sponsor and the project team will remain blinded during the ongoing safety data review. Interim PK/PD analyses will be conducted by an unblinded designee.

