5.2 Independent Data Monitoring Committee

An Independent Data Monitoring Committee (IDMC) will assess the overall status of the study and the safety of subjects. An IDMC charter will be developed to govern IDMC activities which will pre-specify the rules for safety reporting and safety analyses to be presented to the IDMC. The IDMC will make formal recommendations about the conduct of the study and safety of study participants following each IDMC meeting.

In general, it is anticipated that the IDMC will be asked to perform a safety review in the case of thromboembolic events or serious unexpected adverse reactions occurring in ≥ 2 subjects in any single Cohort in the Core Phase.

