8.3 Permitted ITP Concomitant Background Medications

The following medications are permitted as concomitant background medications as long as they are taken at a stable dose for the specified amount of time prior to Day 1/Visit 2. The dose/frequency as well as any dose changes must be recorded in the eCRF.

- Corticosteroids or azathioprine/6-mercaptopurine taken at a stable dose for at least 30 days before Day 1/Visit 2.
- MMF, CsA, sirolimus, or danazol taken at a stable dose for at least 90 days before Day 1/Visit 2.

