7.5.2 Adverse Events

Adverse events (AEs) will be coded using MedDRA version 23.0 or higher and will be classified by SOC and PT of MedDRA. The coding may be updated according to newly released versions of the dictionary. Severity of AEs will be graded according to Common Terminology Criteria for Adverse Events (CTCAE) v5.0.

A treatment emergent adverse event (TEAE) is defined as any AE that occurs after administration of the first dose of study drug.

AEs are classified as related or not related to the study drug based on investigator assessment. AEs with missing or unknown relationship to the study drug will be considered as related AEs.

TEAEs with starting date prior to the first dose date in the Open Label Extension Phase will be classified as TEAEs in the Core Phase. TEAEs with starting date on or after the first dose date in the Open Label Extension Phase will be classified as TEAEs in the Open Label Extension Phase. An overall summary of TEAEs will be provided for each phase and the entire study including:

• Any TEAE

- Any related TEAE
- Any Grade 3-5 TEAE
- Any TEAE leading to study discontinuation
- Any TEAE leading to drug withdrawn
- Any TEAE leading to dose reduction/interruption
- Any serious TEAE
- Any serious TEAE by relationship to study drug (related, unrelated)
- Any death
- Any AESI (AE of special interest) (Thromboembolic events, CTCAE Grade ≥3 Bleeding events)

The following events will be tabulated and summarized. The output will be sorted by decreasing frequency of PT within SOC which is sorted alphabetically in overall events.

- TEAEs by SOC and PT
- TEAEs by PT
- Drug-related TEAEs by SOC and PT
- Drug-related TEAEs by PT
- TEAEs by maximum toxicity grade, SOC and PT
- TEAEs leading to study discontinuation by SOC and PT
- Serious TEAEs by SOC and PT
- Drug-related serious TEAEs by SOC and PT
- AESIs by AESI category and PT

Two categories for Adverse Events of Special Interest (AESI) will be summarized and are defined based on terms in Standardized MedDRA Queries (SMQs) from MedDRA v26.1 or later:

- Thromboembolic events Any thrombotic or embolic event, whether arterial or venous SMQ = Embolic and thrombotic events
- Bleeding Events Any clinically significant blood loss [e.g., bleeding events with CTCAE grade 3+ (based on AE severity [AESEV]>=3] - SMQ = Haemorrhage terms (excl laboratory terms)

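### The two relatedness definitions leave out events with plausible timing and another possible cause, and the related class carries two different thresholds

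*Protocol*

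**What the plan says.** Protocol section 10.1.2.2 asks the investigator for one of two answers, each defined by two conditions joined by 'and'.

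- **No (unrelated):** the timing "rules out a causal relationship and another cause (e.g., concomitant drugs, therapies, complications, etc.) is suspected".
- **Yes (related):** the timing "is consistent with a causal relationship and no other cause (e.g., concomitant drugs, therapies, complications, etc.) can be identified".

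Directly under Yes, the section adds: "The definition implies a reasonable possibility of a causal relationship between the event and the study drug". It explains this as facts or arguments that point towards causality. A list of further factors follows, covering timing, disease, other drugs, class effects, stress and pharmacology. On other drugs, it says they "should be examined to determine whether any of them might be recognized to cause the event in question". The list does not say which answer results when such a cause is found.

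The answer is then used elsewhere. Protocol section 5.1 says "new enrollment may be paused for any serious unexpected and related AEs that occur". Section 5.2 anticipates a committee safety review for "thromboembolic events or serious unexpected adverse reactions occurring in" at least two subjects in a single Core Phase cohort. SAP section 7.5.2 says "AEs are classified as related or not related to the study drug based on investigator assessment", and counts a missing or unknown relationship as related.

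**The concern.** Each definition sets its two conditions together, so they do not cover all events between them. The gap falls on a case that matters: the drug could have caused the event, and so could something else. Such alternatives are built into this trial. The subjects have ITP, and Protocol section 8.3 says: "The following medications are permitted as concomitant background medications", naming corticosteroids, azathioprine/6-mercaptopurine, MMF, cyclosporine, sirolimus and danazol. Section 8.6 adds rescue corticosteroids, immunoglobulins and platelet transfusion.

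The related class also has two thresholds. The bullet requires that no other cause be identifiable. The sentence beneath it requires only a reasonable possibility. An event can pass the second and fail the first, and sites are not told which governs. Across about 50 sites, the same clinical picture could be recorded differently. Some events with a reasonable possibility of causality could be recorded as not related and then fall outside the rules that look at relatedness.

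**Working it through.** There is no figure to reproduce and no arithmetic. The check crosses the two criteria in section 10.1.2.2 and then traces where relatedness is used.

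**Step 1. Cross the two criteria.**

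| Timing | Another cause | Literal Yes | Literal No | Class |
|---|---|---|---|---|
| Consistent | None identified | Met | Not met | Related |
| Ruled out | Suspected | Not met | Met | Not related |
| Consistent | Present | Fails on cause | Fails on timing | None |
| Ruled out | None | Fails on timing | Fails on cause | None |

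Two of the four combinations have no class. The last row does no practical harm, since an event whose timing excludes the drug would be called not related by anyone. The third row is the real gap.

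**Step 2. Apply the reasonable-possibility sentence to row three.** The timing fits, and facts or arguments may point to the drug even though another cause exists. Such an event may be related under that sentence, but it cannot be under the bullet above it. The two texts are not strictly contradictory, because any event that meets the bullet also meets the sentence. They are two different thresholds for one class.

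**Step 3. Trace the uses of relatedness.**

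| Rule | Depends on causality? |
|---|---|
| Enrollment pause (Protocol 5.1) | Yes |
| Committee review, non-thromboembolic reactions (5.2) | Yes |
| Committee review, thromboembolic events (5.2) | No |
| SAE reports from consent to discharge (10.4.1) | No |
| SAE reports after discharge (10.4.1) | Yes |
| AESI reports (10.2) | No |
| SUSAR safety reports (10.6) | Possibly: they require a suspected reaction, but the protocol does not say whether the sponsor makes its own causality assessment |
| Drug-related TEAE and serious TEAE tables (SAP 7.5.2) | Yes |
| Tables of all TEAEs, serious TEAEs and AESIs (SAP 7.5.2) | No |

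**Step 4. Test the SAP safeguard.** Counting a missing or unknown relationship as related helps the tables when the field is blank or unknown. It does not change an entered No, and it acts at analysis, so it does not reach the enrollment pause or the committee trigger while the trial runs.

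**The case against.** The strongest reply is that the direction of error is not established. Read literally, the No definition is as strict as the Yes definition, so a row-three event cannot properly be entered as No either. A site might choose Yes on the reasonable-possibility sentence, choose No, or leave the field blank, in which case the SAP counts the event as related. The factor list also invites weighing; its entry on stress speaks of a better explanation. This stands in part: entry as No is possible, not certain, and the finding is inconsistency with some risk of under-classification.

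A second reply is that the causality-dependent rules are soft. The pause is optional, the committee trigger is described as what is generally anticipated, and section 11.2.4 has the committee monitoring safety at regular intervals in any case. The SAP also tabulates all TEAEs by treatment in the Core Phase, so an excess on drug would be visible without any causality judgement. This limits the consequence, but does not make the definitions usable.

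Two stronger readings are tempting. A reader might infer that reactions go unreported. The documents do not support that: section 10.4.1 sends every in-study SAE to the sponsor within 24 hours whatever its presumed cause, and section 10.2 puts AESIs on the same timeline. A reader might also infer from Protocol Table 1 that the unclassified case is the commonest one, because headache (14%), contusion (18%) and epistaxis (18%) occurred on placebo. Those are incidences in pooled adult trials with 22 placebo subjects. They do not give the share of on-drug events with an identifiable other cause, and no document gives that share.

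**Conclusion.** The point holds as a defect of definition. Section 10.1.2.2 has two classes that are not exhaustive and two thresholds on one of them. Events with plausible timing and another possible cause have no stated class, so sites may differ and some events that meet the reasonable-possibility standard can be recorded as not related.

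The exposure is confined to the causality-dependent rules traced above; SUSAR handling is included only as a possibility. No magnitude is claimed. That such events will arise at all is an inference from the disease, the permitted background drugs and the rescue therapies. The conclusion also assumes that the eCRF offers the same two answers as the protocol; the eCRF and its completion guide are not among the documents. The change should be made, since relatedness feeds a pause rule in a trial that opens enrollment to progressively younger children.

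**What to change.** Replace the two bullets in section 10.1.2.2 with complementary definitions on the standard the section already states:

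- **Related:** there is a reasonable possibility that study drug caused or contributed to the event, whether or not another cause is also possible.
- **Not related:** there is no reasonable possibility that study drug caused or contributed to the event.

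Keep the existing factors, labelled as considerations to weigh and not as conditions that bar either answer. Carry the same wording into the eCRF completion guide. The SAP needs no change, because its two classes and its rule for missing or unknown relationship work with these definitions.

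The cost is two sentences of protocol text plus guidance. Under section 13.3 an amendment goes through the same review and approval as the original protocol. Some more events will be classed as related, with some more safety reports as a result. Because cohorts enroll in sequence, a mid-study change could leave them assessed under different definitions; the study report should then state which events were assessed before the amendment, so that drug-related tables are not compared across cohorts without that caveat.

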10.2 Adverse Events of Special Interest

The purpose for specifying AESI is to enable further characterization of the clinical course and management of specific events. The Investigator will monitor each subject for clinical and laboratory evidence of pre-defined AESIs throughout their participation in the study, and will report all AESIs listed below within the same timeframe as an SAE (Section 10.4). An AESI may or may not be the consequence of treatment with avatrombopag.

The AESI defined in this protocol include:

- Thromboembolic events (any thrombotic or embolic event, whether arterial or venous).
- Bleeding events (any clinically significant blood loss [e.g., WHO Grade 2 or higher]).

These events will be recorded on the AE eCRF page. The Investigator will assess and record any additional information on the AESI in detail on a SAE form (whether or not the event meets seriousness criteria in Section 10.3), to be submitted within 24 hours of awareness of the event. During the course of the study, additional AESI may be identified and communicated by the Sponsor.

10.3 Serious Adverse Events

An AE or adverse reaction is considered serious if, in the view of either the Investigator or Sponsor, it results in any of the following outcomes:

- Death,
- A life-threatening AE,
 - ONOTE: An AE or adverse reaction is considered "life-threatening" if, in view of either the Investigator or Sponsor, its occurrence places the subject at immediate risk of death. It does not include an event that, had it occurred in a more severe form, might have caused death.
- Requires hospitalization or prolongation of existing hospitalizations,
 - ONOTE: Any hospital admission will be considered an inpatient hospitalization, even if admitted and discharged on the same day. An emergency room visit without hospital admission will not be recorded as an SAE under this criterion, nor will hospitalization for a procedure scheduled or planned before signing of informed consent/assent. However, unexpected complications and/or prolongation of hospitalization that occur during elective surgery should be recorded as AEs and assessed for seriousness. Admission to the hospital for social or situational reasons (i.e., no place to stay, live too far away to come for hospital

visits) will not be considered inpatient hospitalizations. Hospitalization due to expected recovery time for the planned procedure will not be counted as an SAE.

- A persistent or significant disability/incapacity or substantial disruption of the ability to conduct normal life functions,
- A congenital anomaly/birth defect, or
- An important medical event.
 - ONOTE: Important medical events that may not result in death, be life-threatening, or require hospitalization may be considered an SAE when, based upon appropriate medical judgment, they may jeopardize the subject and may require medical or surgical intervention to prevent one of the outcomes listed above. Examples of such medical events include allergic bronchospasm requiring intensive treatment in an emergency room or at home, blood dyscrasias or convulsions that do not result in inpatient hospitalizations, or the development of drug dependency.

10.4 Serious Adverse Event Reporting – Procedures for Investigators

10.4.1 Initial Reports

All SAEs, regardless of causal assessment, occurring from the time of informed consent/assent until discharge from the study must be reported to the Sponsor as directed on the SAE reporting form within 24 hours of the knowledge of the occurrence (this refers to any AE that meets any of the aforementioned serious criteria). All SAEs that the Investigator considers causally related to study drug occurring after discharge from the study must be reported to the Sponsor.

To report the SAE, complete the appropriate form for the study and submit to the Sponsor as instructed on the form. It is very important that the form be filled out as completely as possible at the time of the initial report. This includes the Investigator's assessment of causality. The Investigator must notify his/her IRB/IEC of the occurrence of the SAE, in writing, if required by their institution. A copy of this communication must be forwarded to the Sponsor to be filed in the Sponsor's Trial Master File.

The detailed contact information for reporting of SAEs is provided in the Investigator Study File.

10.4.2 Follow-up Reports

The Investigator must continue to follow the subject until the SAE has subsided or until the condition becomes chronic in nature, stabilizes (in the case of persistent impairment), the subject is lost to follow-up, or the subject dies.

Any follow-up information received on SAEs should be forwarded within 1 business day of its receipt. If the follow-up information changes the Investigator's assessment of causality, this should also be noted on the appropriate SAE follow-up form. Preliminary SAE reports should be followed as soon as possible by detailed descriptions including copies of hospital case reports, autopsy reports, and other documents requested by the Sponsor.

Within 24 hours of receipt of follow-up information, the Investigator must update the appropriate form for the study and submit any supporting documentation (e.g., subject discharge summary or autopsy reports) via fax or e-mail.

10.5 Pregnancy Reporting

If the subject becomes pregnant during the study or within 30 days of discontinuing study drug, the Investigator should report the pregnancy to the Sponsor on the Pregnancy Report Form within 24 hours of being notified.

A subject becoming pregnant while on study drug will immediately be withdrawn from the study and early termination study procedures will be performed.

The subject should be followed by the Investigator until completion of the pregnancy. If the pregnancy ends for any reason before the anticipated date, the Investigator should notify Sobi Pharmacovigilance, or its agent, by completing and forwarding the Pregnancy Report Form with the updated information within 24 hours of being notified. At the completion of the pregnancy, the Investigator will document the outcome of the pregnancy. If the outcome of the pregnancy meets the criteria for immediate classification as an SAE (i.e., postpartum complication, spontaneous abortion, stillbirth, neonatal death, or congenital anomaly), the Investigator should follow the procedures for reporting an SAE and also update the Pregnancy Report Form.

10.6 Regulatory Reporting Requirements for Serious Adverse Events

Regulatory reporting requirements for SAEs include:

- Prompt notification by the Investigator to the Sponsor, or designee, of an SAE is essential so that legal obligations and ethical responsibilities towards the safety of subjects and the safety of a study intervention under clinical investigation are met.
- The Sponsor has a legal responsibility to notify both the local regulatory authority and other regulatory agencies about the safety of a study intervention under clinical investigation. The Sponsor, or designee, will comply with country-specific regulatory requirements relating to safety reporting to the regulatory authority, IRB/IEC, and Investigators.
- Investigator safety reports must be prepared for suspected unexpected serious adverse reactions (SUSARs) according to local regulatory requirements and Sponsor policy. These safety reports will be forwarded to Investigators as necessary.
- An Investigator who receives an Investigator safety report describing as SUSAR or other specific safety information (e.g., summary or listing or SUSARs) from the Sponsor will review the report and file it along with the Investigator's Brochure (IB) and will notify the IRB/IEC, if appropriate, according to local requirements.

